#### 16.4 Analytic plan for primary objective:

Toxicities will be tabulated by type and grade. A point estimate and its 95% confidence interval of the primary endpoint will be calculated and presented based on a Bernoulli distribution.

#### 16.5 Analytic plan for secondary objectives:

- PFS will be measured from the date of initiation of treatment to the first of documented progression or death; and will be estimated using the Kaplan-Meier method. PFS is expected to be comparable to that seen with 4/2 (11 month median); however if the upper bound of the interval is less than 8 months this will be taken as an indication that the efficacy of 2/1 is inferior to that of 4/2.
- Toxicities will be tabulated by type and grade, and the incidence of all  $\geq$  grade 3 toxicities will be calculated by CTCAE v 4.03 along with a 95% confidence interval
- The percentage of patients who underwent one or more dose reductions, dose interruptions and/or treatment delays will be estimated along with a 95% confidence interval. The number of patients who discontinue treatment due to unacceptable toxicities will be recorded, and reported as a percentage of the total number of enrolled patients along with 95% confidence interval.
- Health-related quality of life (HRQOL) will be assessed by FACT-G questionnaires as a secondary endpoint. Questionnaires will be administered at baseline, week 12, week 24 and week 36. Descriptive summary statistics will be calculated for all continuous variables (means, standard deviations, medians, ranges, percentage of patients scoring in the highest category for each item) for the items in the subscales each time point. The mean trajectories of each group over time will be plotted for the total scores, along with scores for physical well-being, emotional well-being, functional well-being, and renal-specific scales for FACT-G.

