#### 3.0 STUDY DESIGN

# 3.1 Study schema

This is a single arm phase II study of sunitinib administered to treatment-naïve patients with clear cell mRCC. Patients will be treated with sunitinib at a starting dose of 50mg 2/1 with schedule/dose modifications for toxicity and treated until RECIST-defined progressive disease or unacceptable toxicity. Adverse events will be graded and categorized using CTCAE version 4.03 criteria. Staging studies will be assessed per RECIST v 1.

Sunitinib starting dose 50 mg by mouth daily given for 2 weeks "on" followed by 1 week "off" 1 cycle=6 weeks

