# 8.3 Reporting Procedures for All Adverse Events

All participating investigators will assess the occurrence of AEs throughout the subject's participation in the study, beginning at the time of initiation of treatment. Subjects will be followed for toxicity for 30 days after treatment has been discontinued or until death, whichever occurs first. The clinical course of each event will be followed until resolution, stabilization, or until it has been determined that the study treatment or participation is not the cause.

The investigator is responsible for ensuring that all adverse events observed by the investigator or reported by the subject which occur after the subject has initiated treatment are fully recorded in the subject's case report form, subject's medical records, and/or any other institutional requirement. Source documentation must be available to support all adverse events.

A laboratory test abnormality considered clinically relevant (e.g., causing the subject to withdraw from the study), requiring treatment or causing apparent clinical manifestations, or judged relevant by the investigator, should be reported as an adverse event.

The investigator will provide the following for all adverse events:

- Description of the event
- Date of onset and resolution
- Grade of toxicity
- Attribution of relatedness to the investigational agent
- Action taken as a result of the event
- Outcome of event

In this study, descriptions and grading scales found in the NCI Common Terminology Criteria for Adverse Events (CTCAE) version 4.03 will be utilized for AE reporting, available at: http://evs.nci.nih.gov/ftp1/CTCAE/CTCAE 4.03 2010-06-14 QuickReference 8.5x11.pdf

Investigative sites will report adverse events to their respective IRB according to the local IRB's policies and procedures in reporting adverse events.

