#### 10.2 Rationale

With the availability of several new targeted agents that prolong survival in mRCC, there is increasing emphasis on patient preferences based on treatment related quality of life. Two recent randomized trials, COMPARZ and PISCES (pending publication), demonstrated differences in QOL amongst sunitinib and its active comparator, pazopanib [19, 20]. The impact of treatment related toxicities on patients' QOL while receiving sunitinib on the 2/1 schedule is thus an important end-point of interest.

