#### 10.4 Data analyses

The end-point for all three PROs would be the mean score at each time point-baseline, week 12, week 24 and week 36. Descriptive summary statistics will be calculated for all continuous variables (means, standard deviations, medians, ranges, percentage of patients scoring in the highest category for each item) for the items in the subscales each time point. The mean trajectories of each group over time will be plotted for the total scores, along with scores for physical well-being, social well-being, emotional well-being and functional well-being-specific scales for FACT-G.

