# 16.2 Definition of secondary outcomes/endpoints:

- Progression-free survival (PFS) defined as the time from treatment initiation to disease progression using RECIST v 1 or death.
- Incidence of all ≥grade 3 toxicities per CTCAE version 4.03 criteria, defined as the percentage of patients who experience any grade 3 or greater toxicity that is possibly, probably, or definitely related to study therapy.
- Dose reductions, dose interruptions, dose delays will be recorded using pill diaries
  maintained by patients that will be reviewed and recorded at each visit. This outcome will be
  reported as the percentage of patients who underwent one or more dose reductions, dose
  interruptions and/or treatment delays. The number of patients who discontinue treatment due
  to unacceptable toxicities will be recorded, and reported as a percentage of the total number
  of enrolled patients.
- Changes in the patient reported outcomes in FACT-G (general) scale during treatment on schedule 2/1
- Changes in circulating DNA levels with antiangiogenic treatment
- Correlation of tumor associated macrophages (TAM) with response to therapy

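### The FACT-G plan refers to undefined groups, summarises visit scores instead of within-patient change, and never relates FACT-G to toxicity

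*Combined protocol and SAP*

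**What the plan says.** Section 3.1 states: "This is a single arm phase II study of sunitinib". Section 10.2, the rationale for the patient-reported outcomes, says: "The impact of treatment related toxicities on patients' QOL while receiving sunitinib on the 2/1 schedule is thus an important end-point of interest". Section 2.2 lists only the assessment of patient-reported outcomes as an objective. Section 16.2 gives the formal secondary endpoint: "Changes in the patient reported outcomes in FACT-G (general) scale during treatment on" schedule 2/1.

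The analysis appears in Sections 10.4 and 16.5. Section 10.4 sets the target: "The end-point for all three PROs would be the mean score at each time point". Both sections then plan descriptive statistics for the items at baseline and weeks 12, 24 and 36, including the "percentage of patients scoring in the highest category for each item". Both add a plot: "The mean trajectories of each group over time will be plotted for the total scores", with subscale scores alongside.

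Section 8.3 requires, for every adverse event, the grade, the attribution and the "Date of onset and resolution". No section uses these data in the FACT-G analysis.

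**The concern.** Three things do not fit together.

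- **Groups.** A plot by group cannot be drawn as written when there is one arm and no other grouping is defined.
- **Change.** The endpoint is change, but the planned summary is the score at each visit. A sequence of visit means is not a mean of within-patient changes once patients leave, because each visit describes a different set of patients.
- **Toxicity.** Section 10.2 takes an interest in how toxicity affects quality of life, yet no table, model or correlation links the two, although the event data are collected.

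At stake is how the quality-of-life result is read. A whole-cohort curve mixes toxicity, disease course and selective drop-out. The primary toxicity conclusion and the PFS rule are not affected.

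**Working it through.** **The plan's own figure.** The only sizing statement (Section 16.3) is that 60 patients give a 95% half-width below 10 points at an observed toxicity rate of 10-15%. Using 1.96 x sqrt(p(1-p)/60), the half-width is 7.6 points at 10% and 9.0 at 15%. Exact intervals give 8.4 and 9.7. The figure reproduces. There is no sizing for FACT-G.

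**Visit means against within-patient change.** Assumptions, not in the plan: only progression-free patients complete forms, and PFS is exponential. Week 36 is 252 days, or 8.28 months.

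- With the 11-month median in Section 16.5, 60 x exp(-ln2 x 8.28/11) = 35.6 patients remain.
- With an 8-month median (the PFS threshold in that section), 29.3 remain.

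If those who leave had baseline scores lower by D than those who stay, and nobody's score changes, the visit mean still rises by D x (share who left): D x 24.4/60 = 0.41D, or D x 30.7/60 = 0.51D. For D = 0.5 SD that is 0.20-0.26 SD, about the size of the full-cohort 95% half-width of 1.96/sqrt(60) = 0.25 SD. Mean within-patient change would correctly be zero.

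**What a toxicity split can show.** For groups of a and b patients, the 95% half-width in SD units is 1.96 x sqrt(1/a + 1/b). For comparison with the whole-cohort mean, assume a 10-point loss in affected patients and an SD of change of 15; neither figure is in the documents. The cohort mean then shifts by 10p with SE 15/sqrt(60) = 1.94. The split difference is 10 with SE 15 x sqrt(1/a + 1/b). The ratio of the two signals is sqrt((1-p)/p), whatever loss and common SD are assumed.

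| Share affected, p | Groups | Split half-width (SD) | Cohort shift / SE | Split difference / SE | Ratio |
|---|---|---|---|---|---|
| 10% | 6 v 54 | 0.84 | 0.52 | 1.55 | 3.0 |
| 15% | 9 v 51 | 0.71 | 0.77 | 1.84 | 2.4 |
| 30% | 18 v 42 | 0.55 | 1.55 | 2.37 | 1.5 |
| 40% | 24 v 36 | 0.52 | 2.07 | 2.53 | 1.2 |
| 50% | 30 v 30 | 0.51 | 2.58 | 2.58 | 1.0 |

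The first two rows use the plan's rate for the grade 3 or worse composite. The others bracket a grade 2 or worse share, which the documents do not give. Under the attrition assumption with an 11-month median, the grade 3 or worse group at week 36 is about 4-5 patients, with a half-width of 1.09-0.92 SD.

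**When FACT-G is asked.** Weeks 12, 24 and 36 are days 84, 168 and 252, that is 2, 4 and 6 cycles of 42 days, so each falls on day 42 of a cycle. Section 6.1 makes week 6 a treatment break, and the questionnaire in Appendix 3 asks about the past 7 days. For a patient on the starting schedule and seen on time, the recall period therefore lies in the off-drug week. The 5-day visit window and the alternative schedules in Table 3a allow some exceptions.

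**The case against.** The strongest reply is that the planned description answers the endpoint as defined, and that a toxicity split is an optional extra. Much of this stands, and it limits the point in four ways.

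- A reader might infer that the plan cannot show any impact of toxicity on quality of life. The documents do not support that. The item summaries cover GP5, where patients rate how much side effects bother them, and GP1 on lack of energy, and Physical Well-Being is plotted. These are whole-cohort summaries, but they are informative.
- A reader might infer that Section 10.2 makes this impact the quality-of-life endpoint. It is a rationale and calls it one important endpoint. Section 16.2 does not mention toxicity.
- A reader might infer that the overall mean dilutes any effect to almost nothing. That needs the loss to be confined to the 10-15% with grade 3 or worse events. At 40% affected, the cohort mean moves about 2.1 SE against 2.5 SE for the split, a modest gain. Table 1 shows 54% all-grade fatigue in one series on the 2/1 schedule, so a wider share is plausible.
- A reader might infer that a split isolates toxicity. It does not. Section 1.3.6 says severity appears to track higher exposure and/or lower performance status, so the groups would differ in other ways. Classifying by onset alone also counts events that have long resolved. Nor can a split recover on-drug burden that was not sampled.

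It is also true that no decision rule attaches to FACT-G, and nothing in the documents says a flat curve will be taken as reassurance. What the reply does not answer is that the groups are undefined, that change is not summarised as change, and that the stated interest in toxicity has no direct analysis.

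**Conclusion.** The point holds in a limited form. As written, the group trajectories cannot be produced; the planned summaries do not match the endpoint of change; and the Section 10.2 interest is addressed only indirectly. The undefined groups and the missing toxicity analysis follow from the text alone. The size of the drop-out effect (0.20-0.26 SD for D = 0.5 SD) rests on the assumed attrition and on D.

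The toxicity split would be observational and imprecise: about 6-9 patients with grade 3 or worse events and a half-width of about 0.7-0.8 SD before attrition. It gives a direct but limited answer. The off-drug timing limits every FACT-G analysis in this trial, with or without the split. The change is worth making because it costs little.

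**What to change.** In Sections 10.4 and 16.5:

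1. Delete the reference to groups.
2. Report mean within-patient change from baseline in the FACT-G total and Physical Well-Being scores at weeks 12, 24 and 36, with 95% intervals and the number contributing at each visit. Report GP5 explicitly at each visit.
3. Add a descriptive table of the same change by whether related fatigue, hand-foot syndrome or diarrhea of grade 2 or worse (and, separately, grade 3 or worse) began on or before the visit. Use resolution dates to separate ongoing from resolved events. Label the table observational and imprecise.
4. State that the scheduled post-baseline assessments fall at the end of an off-drug week, so a flat curve must not be read as no effect of toxicity on quality of life.
5. While editing, reconcile the mention of three instruments in 10.4 and the renal-specific scales in 16.5 with the single instrument administered, and the social well-being scale that 10.4 lists and 16.5 omits.

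The cost is wording and one extra table from data already collected. The drawback is a small grade 3 or worse group with wide intervals.

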# **APPENDIX 1: PILL DIARY**

			Sutent Diary S	heet		
			Sutche Diary S	nicet		
utent	_mg capsule					
ke a total of	capsi	ule(s) daily for _	days wi	th or without fo	ood then	days off thera
Date	Date	Date	Date	Date	Date	Date
Time	Time		Time	Time		25
Sutent	Sutent	Sutent	Sutent	Sutent	Sutent_	Sutent_
Date	Date	Date	Date_	Date	Date	Date
Time	Time	Time	Time	Time_	Time	Time
Sutent	Sutent	Sutent	Sutent	Sutent	Sutent	Sutent
Date	Date	_ Date	Date	Date	Date	Date
Time	Time	Time	Time_	Time	Time	Time
Sutent	Sutent	Sutent	Sutent	Sutent	Sutent	Sutent
Date	Date	_ Date	Date	_ Date	_ Date	Date
Time	Time	Time	Time	Time	Time	Time
Sutent	Sutent	Sutent	Sutent	Sutent	Sutent	Sutent
Date	Date	_ Date	Date	_ Date	_ Date	_ Date
Time	Time	Time	Time	Time	Time_	Time
Sutent	Sutent	Sutent	_ Sutent	Sutent	Sutent	Sutent
Date	Date	_ Date	Date	_ Date	_ Date	_ Date
Time	Time	Time	Time	Time	Time	Time
Sutent	Sutent	Sutent	_ Sutent	Sutent	Sutent	Sutent
s diary sheet	to every appo	ointment				

# **APPENDIX 2: BLOOD PRESSURE LOG**

DATE Month/Date	TIME		BLOOD PRESSURE
	AM	PM	
	AM	PM	
	AM	PM	*
	AM	PM	
	AM	PM	22
	AM	PM	
	AM	PM	5
	AM	PM	
	AM	PM	99
	AM	PM	
,	AM	PM	
	AM	PM	

\*\*\* Please bring this diary card to all of your appointments

# **Patient Signature and Date:**

# **APPENDIX 3: FACT-G questionnaire**

Below is a list of statements that other people with your illness have said are important. Please circle or mark one number per line to indicate your response as it applies to the past 7 days.

	PHYSICAL WELL-BEING	Not at all	A little bit	Some- what	Quite a bit	Very much
GP1	I have a lack of energy	0	1	2	3	4
GP2	I have nausea	0	1	2	3	4
GP3	Because of my physical condition, I have trouble meeting the needs of my family	0	1	2	3	4
GP4	I have pain	0	1	2	3	4
GP5	I am bothered by side effects of treatment	0	1	2	3	4
GP6	I feel ill	0	1	2	3	4
GP7	I am forced to spend time in bed	0	1	2	3	4
	SOCIAL/FAMILY WELL-BEING	Not at all	A little bit	Some- what	Quite a bit	Very much
GS1	I feel close to my friends	0	1	2	3	4
GS2	I get emotional support from my family	0	1	2	3	4
GS3	I get support from my friends	0	1	2	3	4
GS4	My family has accepted my illness	0	1	2	3	4
GS5	I am satisfied with family communication about my illness	0	1	2	3	4
GS6	I feel close to my partner (or the person who is my main support)	0	1	2	3	4
Q1	Regardless of your current level of sexual activity, please answer the following question. If you prefer not to answer it, please mark this box and go to the next section.					
GS7	I am satisfied with my sex life	0	1	2	3	4

# Please circle or mark one number per line to indicate your response as it applies to the past 7 days.

	EMOTIONAL WELL-BEING	Not at all	A little bit	Some- what	Quite a bit	Very much
GE1	I feel sad	0	1	2	3	4
GE2	I am satisfied with how I am coping with my illness	0	1	2	3	4
GE3	I am losing hope in the fight against my illness	0	1	2	3	4
GE4	I feel nervous	0	1	2	3	4
GE5	I worry about dying	0	1	2	3	4
GE6	I worry that my condition will get worse	0	1	2	3	4
	FUNCTIONAL WELL-BEING	Not at all	A little bit	Some- what	Quite a bit	Very much
GF1	FUNCTIONAL WELL-BEING  I am able to work (include work at home)	at all			_	·
GF1		at all	bit	what	a bit	much
	I am able to work (include work at home)	o o	bit 1	what	a bit	much 4
GF2	I am able to work (include work at home)  My work (include work at home) is fulfilling	0 0 0	bit 1  1	what 2  2	3 3	much 4 4
GF2 GF3	I am able to work (include work at home)  My work (include work at home) is fulfilling  I am able to enjoy life	0 0 0 0	bit  1  1  1	2 2 2	3 3 3	4 4 4
GF2 GF3 GF4	I am able to work (include work at home)	0 0 0 0	bit  1 1 1 1	2 2 2 2	3 3 3 3 3	4 4 4 4
